5.4.1.2.5. INCB059872 Dose Modifications

Table 14 describes INCB059872 dose reductions that may occur due to any related AEs. Dose reductions should occur in a step-wise fashion from the initial starting dose of the cohort, and a maximum of 2 dose reductions of INCB059872 are allowed for the management of an AE, regardless of the initial starting dose. If an AE recurs/does not return to baseline after the second dose reduction of INCB059872, then the subject must permanently discontinue INCB059872. The lowest permissible dose of INCB059872 is 1 mg QoD. If a subject does not tolerate 1 mg QoD, alternative dose schedules may be evaluated.

Table 14: INCB059872 Dose Reductions

Dose Level
3 mgQoD
2 mg QoD/1 mg QD ^a
1 mgQoD

Table 15: Dose Modification Guidelines for Drug-Related Adverse Events (Treatment Group A)

Toxicity	Grade	Hold Treatment (Y/N)	Timing for Treatment Restart	Dose/Schedule for Treatment Restart			Discontinue Subject (After Medical Monitor Consultation)
				Azacitidine	Epacadostat	Pembrolizumab	
Hematologic toxicity	1, 2	No	N/A	N/A	N/A	N/A	N/A
	3	Hold azacitidine	Toxicity resolves to Grade 1 or baseline.	Restart at same dose if the toxicity resolves within 7 days.	N/A	N/A	N/A
	4	Yes	Toxicity resolves to Grade 1 or baseline.	Restart at 1 dose level lower if the toxicity resolves within 7 days.	Reduce dose by 1 dose level.	Restart at same dose for the following events: Grade 4 neutropenia lasting 7 days, Grade 4 lymphopenia or leukopenia. For all other Grade 4 hematologic toxicities, treatment with pembrolizumab may not be restarted.	Toxicity does not resolve within 6 weeks of last infusion. Permanent discontinuation should be considered for any severe or life-threatening event.
Nonhematologic toxicity Note: Exception to be treated to similar Grade 1 toxicity: - Grade 2 alopecia - Grade 2 fatigue - Grade 3 rash in the absence of desquamation, without mucosal involvement, not requiring systemic steroids, and that resolves to Grade 1 within 14 days. For additional information regarding AE with potential immune etiology, see Section 5.4.1.3.	1	No	N/A	N/A	N/A	N/A	N/A
	2	Consider holding for persistent symptoms	Toxicity resolves to Grade 1 or baseline.	Restart at same dose.	Restart at same dose.	Restart at same dose.	Toxicity does not resolve within 6 weeks of last infusion.
	3	Yes*	Toxicity resolves to Grade 1 or baseline.	Restart at same dose.	Restart at 1 dose level lower.	Restart at same dose.*	Toxicity does not resolve within 6 weeks of last infusion. Permanent discontinuation should be considered for any severe or life-threatening event.
	4	Yes	Toxicity resolves to Grade 1 or baseline.	Restart at 1 dose level lower.	Restart at 1 dose level lower.	Restart only permitted only as noted. ^b For all other Grade 4 nonhematologic toxicities, treatment with pembrolizumab may not be restarted.	Toxicity does not resolve within 6 weeks of last infusion. Permanent discontinuation should be considered for any severe or life-threatening event.

Note: Subjects who experience a recurrence of the same severe or life-threatening AE at the same grade or greater treatment should be discontinued from study treatment.

* The following exceptions for asymptomatic amylase or lipase do not require a dose delay: Grade 3 amylase or lipase abnormalities that are not associated with symptoms or clinical manifestations of pancreatitis. It is recommended to consult with the medical monitor for Grade 3 amylase or lipase abnormalities.

^b Isolated Grade 4 lipase or amylase abnormalities not associated with symptoms or clinical manifestations of pancreatitis. Medical monitor should be consulted for any Grade 4 amylase or lipase abnormality.

Table 16: Dose Modification Guidelines for Drug-Related Adverse Events (Treatment Group B)

Toxicity	Grade	Hold Treatment (Y/N)	Timing for Treatment Restat1	Dose/Schedule for Treatment Restat1			Discontinue Subject (After Medical Monitor Consultation)
				INCB057643	Epacadostat	Pembrolizumab	
Hematologic toxicity	1, 2	No	N/A	N/A	N/A	N/A	N/A
	3	Hold INCB057643	Toxicity resolves to Grade 1 or baseline.	Restart at 1 dose level lower if the toxicity resolves within 7 days.	N/A	N/A	N/A
	4	Yes	Toxicity resolves to Grade 1 or baseline.	Restart at 1 dose level lower if the toxicity resolves within 7 days. If already at lowest dose, discontinue. If evidence of bleeding, patient should pennisantly discontinue.	Reduce dose by 1 dose level. If already at lowest dose, discontinue	Restart at same dose.	Toxicity does not resolve within 6 weeks of last infhsion. Permanent discontinuation should be considered for any severe or life-threatening event.

Table 16: Dose Modification Guidelines for Drug-Related Adverse Events (Treatment Group B) (Continued)

Toxicity	Grade	Hold Treatment (Y/N)	Timing for Treatment Restat1	Dose/Schedule for Treatment Restat 1			Discontinue Subject (After Medical Monitor Consultation)
				INCB057643	Epacadostat	Pembrolizumab	
Nonhematologic toxicity Note: Exception to be treated to similar Grade 1 toxicity: - Grade 2 alopecia - Grade 2 fatigue - Grade 3 rash in the absence of desquamation, without mucosal involvement, not requiring systemic steroids, and that resolves to Grade 1 within 14 days. For additional information regarding AE with potential immune etiology, see Section 5.4.1.3.	1	No	N/A	N/A	N/A	N/A	N/A
	2	Consider holding for persistent symptoms	Toxicity resolves to Grade 1 or baseline.	Restart at same dose.	Restart at same dose.	Restart at same dose.	Toxicity does not resolve within 6 weeks of last infusion.
	3	Yes	Toxicity resolves to Grade 1 or baseline.	Restart at same dose.	Restart at 1 dose level lower.	Restart at same dose.	Toxicity does not resolve within 6 weeks of last infusion. Permanent discontinuation should be considered for any severe or life-threatening event.
	4	Yes	Toxicity resolves to Grade 1 or baseline.	Restart at 1 dose level lower. If already at lowest dose, discontinue.	Restart at 1 dose level lower. If already at lowest dose, discontinue.	Restart only permitted only as noted. ^b For all other Grade 4 nonhematologic toxicities, treatment with pembrolizumab may not be restarted.	Toxicity does not resolve within 6 weeks of last infusion. Permanent discontinuation should be considered for any severe or life-threatening event.

Note: Subjects who experience a recurrence of the severe or life-threatening AE at the same grade or greater treatment should be discontinued from study treatment.

^a The following exceptions for asymptomatic amylase or lipase do not require a dose delay: Grade 3 amylase or lipase abnormalities that are not associated with symptoms or clinical manifestations of pancreatitis. It is recommended to consult with the medical monitor for Grade 3 amylase or lipase abnormalities.

^b Isolated Grade 4 lipase or amylase abnormalities not associated with symptoms or clinical manifestations of pancreatitis. Medical monitor should be consulted for any Grade 4 amylase or lipase abnormality.

Table 17: Dose Modification Guidelines for Drug-Related Adverse Events (Treatment Group C)

Toxicity	Grade	Hold Treatment (Y/N)	Timing for Treatment Restat1	Dose/Schedule for Treatment Restat 1			Discontinue Subject (After Medical Monitor Consultation)
				INCB059872	Epacadostat	Pembrolizumab	
Hematologic toxicity	1, 2	No	N/A	N/A	N/A	N/A	N/A
	3	Hold INCB059872	Toxicity resolves to Grade 1 or baseline.	Restart at 1 dose level lower if the toxicity resolves within 7 days.	N/A	N/A	N/A
	4	Yes	Toxicity resolves to Grade 1 or baseline.	Restart at 1 dose level lower if the toxicity resolves within 7 days. If already at lowest dose, discontinue. If evidence of bleeding, patient should pennisantly discontinue.	Reduce dose by 1 dose level. If already at lowest dose, discontinue	Restart at same dose.	Toxicity does not resolve within 6 weeks of last infhsion. Permanent discontinuation should be considered for any severe or life-thr-eatening event.

Table 17: Dose Modification Guidelines for Drug-Related Adverse Events (Treatment Group C) (Continued)

Toxicity	Grade	Hold Treatment (Y/N)	Timing for Treatment Restat1	Dose/Schedule for Treatment Restat 1			Discontinue Subject (After Medical Monitor Consultation)
				INCB059872	Epacadostat	Pembrolizumab	
Nonhematologic toxicity Note: Exception to be treated to similar Grade 1 toxicity: - Grade 2 alopecia - Grade 2 fatigue - Grade 3 rash in the absence of desquamation, without mucosal involvement, not requiring systemic steroids, and that resolves to Grade 1 within 14 days. For additional information regarding AE with potential immune etiology, see Section 5.4.1.3.	1	No	N/A	N/A	N/A	N/A	N/A
	2	Consider holding for persistent symptoms	Toxicity resolves to Grade 1 or baseline.	Restart at same dose.	Restart at same dose.	Restart at same dose.	Toxicity does not resolve within 6 weeks of last infusion.
	3	Yes	Toxicity resolves to Grade 1 or baseline.	Restart at same dose.	Restart at 1 dose level lower.	Restart at same dose.	Toxicity does not resolve within 6 weeks of last infusion. Permanent discontinuation should be considered for any severe or life-threatening event.
	4	Yes	Toxicity resolves to Grade 1 or baseline.	Restart at 1 dose level lower. If already at lowest dose, discontinue.	Restart at 1 dose level lower. If already at lowest dose, discontinue.	Restart only permitted only as noted. ^b For all other Grade 4 nonhematologic toxicities, treatment with pembrolizumab may not be restarted.	Toxicity does not resolve within 6 weeks of last infusion. Permanent discontinuation should be considered for any severe or life-threatening event.

Note: Subjects who experience a recurrence of the same severe or life-threatening AE at the same grade or greater treatment should be discontinued from study treatment.

• The following exceptions for asymptomatic amylase or lipase do not require a dose delay: Grade 3 amylase or lipase abnormalities that are not associated with symptoms or clinical manifestations of pancreatitis. It is recommended to consult with the medical monitor for Grade 3 amylase or lipase abnormalities.

^b Isolated Grade 4 lipase or amylase abnormalities not associated with symptoms or clinical manifestations of pancreatitis. Medical monitor should be consulted for any Grade 4 amylase or lipase abnormality.

5.4.1.3. Procedures for Subjects Exhibiting Immune-Related Adverse Events

This section is meant to apply to suspected irAEs from epacadostat, pembrolizumab, or the combination.

Immune-related AEs may be defined as an AE of unknown etiology, associated with drug exposure and consistent with an immune phenomenon. Immune-related AEs may be predicted based on the nature of the pembrolizumab or epacadostat compounds, their mechanism of action, and reported experience with immunotherapies that have a similar mechanism of action. Special attention should be paid to AEs that may be suggestive of potential irAEs. An irAE can occur shortly after the first dose or several months after the last dose of treatment.

If an irAE is suspected, efforts should be made to rule out neoplastic, infectious, metabolic, toxin or other etiologic causes before labeling an AE as an irAE. Subjects who develop a Grade 2 irAE should be discussed immediately with the sponsor.

General recommendations to managing irAEs not detailed elsewhere in the Protocol are detailed in Table 18. Recommendations for management of specific immune-mediated AEs such as pneumonitis (Section 5.4.1.3.1), enterocolitis (Section 5.4.1.3.2), hepatitis (Section 5.4.1.3.3), dermatitis (Section 5.4.1.3.4), neuropathies (Section 5.4.1.3.5), endocrinopathies (Section 5.4.1.3.6), myocarditis (Section 5.4.1.3.7), and other immune-mediated AEs (Section 5.4.1.3.8) are detailed in the sections below.

Table 18: General Approach to Handling Immune-Related Adverse Events

irAE	Withhold/Discontinue Pembrolizumab and Epacadostat	Guidance for Restarting Study Treatment	Supportive Care
Grade 1	No action.	Not applicable.	Provide symptomatic treatment.
Grade 2	May withhold pembrolizumab and epacadostat per investigator's discretion.	May return to treatment if improves to Grade 1 or resolves within 6 weeks. If AE resolves within 4 weeks, subject may restart at the same dose and schedule for both pembrolizumab and epacadostat. For an AE that does not resolve within 4 weeks, epacadostat should be reduced 1 dose level, but pembrolizumab may be restarted at the same dose and schedule. If AE does not resolve within 6 weeks, study treatment with both study drugs should be discontinued or discussed with medical monitor.	Consider systemic corticosteroids in addition to appropriate symptomatic treatment.

Table 18: General Approach to Handling Immune-Related Adverse Events
 (Continued)

irAE	Withhold/Discontinue Pembrolizumab and Epacadostat	Guidance for Restarting Study Treatment	Supportive Care
Grade 3	Withhold or discontinue pembrolizumab and epacadostat. Discontinue if unable to reduce corticosteroid dose to < 10 mg/day of prednisone or equivalent within 6 weeks of toxicity.	Any restart of study treatment must be discussed with medical monitor before restarting treatment.	Systemic corticosteroids are indicated in addition to appropriate symptomatic treatment. May use 1 to 2 mg/kg of prednisone or equivalent per day. Steroid taper should be considered once symptoms improve to Grade 1 and tapered over at least 4 weeks in most cases.
Grade 4	Discontinue pembrolizumab and epacadostat.	Not applicable. Any exceptions require medical monitor approval.	Systemic corticosteroids are indicated in addition to appropriate symptomatic treatment. May use 1 to 2 mg/kg of prednisone or equivalent per day.

5.4.1.3.1. Procedures and Guidelines for Pneumonitis

Subjects with symptomatic pneumonitis should immediately stop receiving pembrolizumab and epacadostat and have an evaluation. The evaluation may include bronchoscopy to rule out other causes such as infection. If the subject is determined to have study drug-associated pneumonitis, the suggested treatment plan is detailed in [Table 19](#).

Table 19: Recommended Approach for Handling Noninfectious Pneumonitis

Study Drug(s) Associated Pnemnonitis	Withhold/Discontinue Pembrolizumab and Epacadostat	Guidance for Restarting Study Treatment	Supportive Care
Grade 1 (asymptomatic)	No action.	Not applicable.	Intervention not indicated.
Grade 2	Withhold pembrolizumab and epacadostat.	
First episode of pneumonitis: If improves to near baseline: Decrease the dose of epacadostat by 1 dose level, and for pembrolizumab, restrut at same dose and schedule subsequent cycles.
 
If not improved after 2 weeks or worsening, pe1manently discontinue pembrolizumab. Discuss with medical monitor if restrut with epacadostat is pennitted.
 
Second episode of pneumonitis: Pe1manently discontinue pembrolizumab and epacadostat if upon rechallenge subject develops pneumonitisGrade 2.
	Systemic corticosteroids are indicated. Taper if necessruy.
Grades 3 and 4	Discontinue pembrolizumab and epacadostat.	Not applicable. Any exceptions require medical monitor approval.	Systemic cmticosteroids rre indicated. The use of infliximab may be indicated as appropriate.

5.4.1.32. Procedures and Guidance for Enterocolitis

Subjects should be carefully monitored for signs and symptoms of enterocolitis (such as diarrhea, abdominal pain, mucus or blood in stool, with or without fever) and of bowel perforation (such as peritoneal signs and ileus). In symptomatic subjects, infectious etiologies should be mled out, and endoscopic evaluation should be considered for persistent or severe symptoms. Recommendations for management of enterocolitis are shown in [Table 20](#).

Table 20: Recommended Approach for Handling Enterocolitis

Study Drug(s) Associated Enterocolitis	Withhold/Discontinue Pembrolizumab and Epcadostat	Guidance for Restarting Study Treatment	Supportive Care
Grade 1	No action.	Not applicable.	All subjects who experience diarrhea should be advised to drink liberal quantities of clear fluids. If sufficient oral fluid intake is not feasible, fluid and electrolytes should be substituted via IV infusion. An antidiarrheal can be started.
Grade 2	Withhold pembrolizumab and epcadostat.	
May return to treatment if improves to Grade 1. If AE resolves within 4 weeks, subject may restart at the same dose and schedule for both pembrolizumab and epcadostat.
 
For an AE that does not resolve within 4 weeks, epcadostat should be reduced 1 dose level, but pembrolizumab may be restarted at the same dose and schedule. If AE does not resolve within 6 weeks, study treatment with both study drugs should be discontinued or discussed with medical monitor.
	An antidiarrheal should be started. If symptoms are persistent for > 1 week, systemic corticosteroids should be initiated (eg, 0.5-1 mg/kg per day of prednisone or equivalent). When symptoms improve to Grade 1, corticosteroid taper should be started and continued over at least 1 month.
Grades 3 and 4	Discontinue pembrolizumab and epcadostat.	Not applicable. Any exceptions require medical monitor approval.	Treatment with systemic corticosteroids should be initiated at a dose of 1 to 2 mg/kg per day of prednisone or equivalent. Systemic corticosteroids are indicated. The use of infliximab may be indicated as appropriate. When symptoms improve to Grade 1, corticosteroid taper should be started and continued over at least 1 month.

5.4.1.3.3. Procedures and Guidance for Hepatitis

Liver chemistry tests (hepatic transaminase and bilirubin levels) should be monitored and signs and symptoms of hepatotoxicity should be assessed before each dose of pembrolizumab and epacadostat. In subjects with hepatotoxicity, infectious or malignant causes should be ruled out, and frequency of LFT monitoring should be increased until resolution. Recommendations for managing hepatitis are shown in Table 21.

Table 21: Recommended Approach for Handling Hepatitis

Study Drug(s) Associated Hepatitis	Withhold/Discontinue Pembrolizumab and Epacadostat	Guidance for Restarting Study Treatment	Supportive Care
Grade 1	No action.	Not applicable.	Increase frequency of LFT monitoring to twice per week until LFTs return to baseline.
Grade 2	Withhold pembrolizumab and epacadostat.	If AE resolves to Grade 1 or baseline within 4 weeks, subject may restart at the same dose and schedule for both pembrolizumab and epacadostat. For an AE that does not resolve within 4 weeks, epacadostat should be reduced 1 dose level but pembrolizumab may be restarted at the same dose and schedule. If AE does not resolve within 6 weeks, study treatment with both study drugs should be discontinued.	Increase frequency of LFT monitoring to twice per week until LFTs return to baseline. If elevation persists for > 1 week, systemic corticosteroids should be initiated (eg, 0.5 mg/kg per day of prednisone or equivalent). When symptoms improve to Grade 1, corticosteroid taper should be started and continued over at least 1 month.
Grades 3 and 4	Discontinue pembrolizumab and epacadostat.	Not applicable. Any exceptions require medical monitor approval.	Increase frequency of LFT monitoring to every 1-2 days. Treatment with systemic corticosteroids should be initiated at a dose of 1 to 2 mg/kg per day of prednisone or equivalent. When symptoms improve to Grade 1, corticosteroid taper should be started and continued over at least 1 month.

5.4.1.3.4. Procedures for Immune-Mediated Dermatitis

Monitor subjects for signs and symptoms of dermatitis such as rash and pruritus. Unless an alternate etiology has been identified, signs or symptoms of dermatitis should be considered immune-mediated. Recommendations for management of dermatitis are shown in [Table 22](#).

Table 22: Recommended Approach for Handling Dermatitis

irAE	Withhold/Discontinue Pembrolizumab and Epacadostat	Guidance for Restarting Study Treatment	Supportive Care
Grade 1	No action.	Not applicable.	For mild to moderate dermatitis, such as localized rash and pruritus, treat symptomatically. Administer topical or systemic corticosteroids if there is no improvement of symptoms within 1 week.
Grade 2	No action.	Not applicable.	For mild to moderate dermatitis, such as localized rash and pruritus, treat symptomatically. Administer topical or systemic corticosteroids if there is no improvement of symptoms within 1 week.
Grades 3 and 4	Withhold epacadostat and pembrolizumab in subjects with moderate to severe signs and symptoms of rash. Permanently discontinue epacadostat and pembrolizumab in subjects with Stevens-Johnson syndrome, toxic epidermal necrolysis, or rash complicated by full thickness dermal ulceration or by necrotic, bullous, or hemorrhagic manifestations.	If AE resolves to baseline within 4 weeks, subject may restart at the same dose and schedule for both pembrolizumab and epacadostat. For an AE that does not resolve within 4 weeks, epacadostat should be reduced 1 dose level, but pembrolizumab may be restarted at the same dose and schedule. If AE does not resolve within 6 weeks, study treatment with both study drugs should be discontinued or discussed with medical monitor.	Administer systemic corticosteroids at a dose of 1 to 2 mg/kg per day of prednisone or equivalent. When dermatitis is controlled, corticosteroid tapering should occur over a period of at least 1 month.

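### For Grade 3-4 rash in Treatment Group A, Protocol Tables 15 and 22 conflict on holding and restarting drug, and the text points to Table 22 without saying that it overrides Table 15

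*Protocol*

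**What the plan says.** Two tables cover rash in Treatment Group A.

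**Table 15 (Section 5.4.1.2, drug-related adverse events).** Among nonhematologic toxicities it names an exception to be handled like Grade 1: "Grade 3 rash in the absence of desquamation, without mucosal involvement, not requiring systemic steroids, and that resolves to Grade 1 within 14 days". Called uncomplicated rash below, this falls under the Grade 1 row, which has no hold. For other Grade 3 events the table holds treatment until Grade 1 or baseline. Epacadostat then follows the instruction "Restart at 1 dose level lower", and pembrolizumab resumes at the same dose. After Grade 4, epacadostat again drops one level. Isolated amylase or lipase elevations aside, the pembrolizumab rule is: "For all other Grade 4 nonhematologic toxicities, treatment with pembrolizumab may not be restarted". The table also carries a pointer: "For additional information regarding AE with potential immune etiology, see Section 5.4.1.3".

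**Table 22 (Section 5.4.1.3.4, immune-mediated dermatitis).** One row serves Grades 3 and 4. Its hold instruction is "Withhold epacadostat and pembrolizumab in subjects with moderate to severe signs and symptoms of rash", with no exception for uncomplicated rash. Permanent discontinuation is reserved for listed complications such as Stevens-Johnson syndrome. Restart reads: "If AE resolves to baseline within 4 weeks, subject may restart at the same dose and schedule for both pembrolizumab and epacadostat". If resolution takes longer than 4 weeks, epacadostat drops one level and pembrolizumab keeps its dose. If the rash has not resolved within 6 weeks, both drugs stop or the case goes to the medical monitor.

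**Which applies.** Section 5.4.1.3 is for suspected immune-related events and sends dermatitis to Section 5.4.1.3.4. That section says that, unless another cause is found, "signs or symptoms of dermatitis should be considered immune-mediated".

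**The concern.** An investigator with a Group A subject who develops Grade 3 or 4 rash can open either table and find a different instruction on holding drug, on the epacadostat restart dose and, at Grade 4, on whether pembrolizumab may resume. Neither table is uniformly the more cautious. Table 22 is stricter on the hold for uncomplicated Grade 3 rash; Table 15 is stricter on both restart questions.

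At stake is the dosing of Group A subjects still on treatment. Section 4.5 lets remaining subjects continue after a database lock, and Section 6.2 allows re-treatment. Rash is not a rare event to leave unclear. Section 1.7.2 reports it as the most frequent treatment-related event in the epacadostat and pembrolizumab doublet study (27% of 60 subjects), with more Grade 3 rash at 300 mg BID than at 100 mg BID. That was a different regimen, so the figures show only that rash is common, not how often these tables would collide.

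**Working it through.** The plan gives no figure to reproduce. The check sets the two tables side by side, tests whether the text chooses between them, and sizes the difference.

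**Step 1: compare the instructions.** The 4-week rows use rash that has returned to baseline, because that meets the restart condition in both tables.

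| Situation | Table 15 | Table 22 | Conflict |
|---|---|---|---|
| Uncomplicated Grade 3: hold | None (as Grade 1) | Both drugs withheld | Yes |
| Other Grade 3: hold | Hold | Both drugs withheld | No |
| Other Grade 3, baseline within 4 weeks: epacadostat | One level lower | May restart at same dose | Yes |
| Other Grade 3, baseline within 4 weeks: pembrolizumab | Same dose | Same dose | No |
| Other Grade 3, resolved between 4 and 6 weeks: epacadostat | One level lower | One level lower | No |
| Grade 4, baseline within 4 weeks: epacadostat | One level lower | May restart at same dose, if no listed complication | Yes |
| Grade 4, resolved within 6 weeks: pembrolizumab | May not restart | May restart at same dose, if no listed complication | Yes |

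**Step 2: does the text choose?** Three sentences lean towards Table 22: the pointer in Table 15, the scope of Section 5.4.1.3, and the presumption in Section 5.4.1.3.4 that rash is immune-mediated. None says that Table 22 replaces Table 15. The pointer offers further information, not an override, and Table 15 keeps its own named rash exception. If every rash without another identified cause goes to Table 22, that exception is left only for rash with some other identified cause, a limit the table does not state.

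**Step 3: does choosing Table 22 settle it?** Not at Grade 4. The other immune-related tables treat Grade 4 as follows.

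- Tables 18 (general), 19 (pneumonitis), 20 (enterocolitis), 21 (hepatitis), 23 (neuropathies) and 24 (endocrinopathies): discontinue both drugs, with exceptions only by medical monitor approval.
- Table 25 (myocarditis): permanently discontinue.
- Table 22: restart allowed without that approval if the rash resolves within 6 weeks and no listed complication is present.

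Table 22 is therefore out of line with its companion tables as well as with Table 15.

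**Step 4: size.** Table 11 gives epacadostat levels of 300, 100, 50 and 25 mg BID. Escalation Cohorts 1 to 3 use 100 or 300 mg BID (Table 1).

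- From 300 mg BID, one level lower is 100 mg BID: 1 − 100/300 = 67% lower.
- From 100 mg BID, one level lower is 50 mg BID: 1 − 50/100 = 50% lower.
- Under Table 22, with baseline reached within 4 weeks, the dose may stay the same: 0% lower.
- The Table 15 step uses one of the two epacadostat reductions allowed by Section 5.4.1.2.2, leaving 2 − 1 = 1.

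**The case against.** **The text already routes rash to Table 22, and the specific rule should beat the general one.** This largely stands. A reader might infer that the protocol gives no guidance on which table applies, and that would be wrong. But routing does not explain why Table 15 keeps its rash exception, and it sends Grade 4 rash to the one table out of line.

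**Table 22 only permits a same-dose restart, so following Table 15 breaches nothing.** True of restart in that direction. In the other, an investigator who uses the permission resumes pembrolizumab where Table 15 forbids it. The hold cannot be reconciled this way: not holding, as Table 15 has it, departs from Table 22.

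**The exception cannot be applied at onset, because it depends on resolution within 14 days.** Also true. It blurs the hold contrast, and is itself a reason to settle the exception.

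**Other controls limit the harm.** These stand. Section 5.4.1.2 calls the dose-reduction rules guidelines, to be used with clinical judgment and medical monitor consultation, and asks for sponsor contact before restart after a delay of more than 14 days. Section 5.4.4 requires permanent discontinuation for a persistent event needing a longer delay, unless the sponsor approves. Unaided choice is thus confined to about the first 14 days. Section 5.4.1.3 also wants Grade 2 immune-related events discussed at once with the sponsor. If that means Grade 2 or above, which is likely but cannot be confirmed from the copy reviewed, Grade 3-4 rash reaches the sponsor too. None of these sections says which dose to use.

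**Conclusion.** Tables 15 and 22 conflict on three points: the hold for uncomplicated Grade 3 rash; the epacadostat dose after other Grade 3 rash, or Grade 4 rash, that returns to baseline within 4 weeks; and pembrolizumab after Grade 4 rash without a listed complication. The text leans towards Table 22 without giving it precedence. The difference is one epacadostat step (67% or 50%) and pembrolizumab barred or resumed after Grade 4. Given the controls above, the point is minor.

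Two stronger readings are tempting, and the documents do not support them.

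- *The tables contradict each other on steroids.* Table 22 says "Administer systemic corticosteroids at a dose of 1 to 2 mg/kg per day of prednisone or equivalent". Table 15 gives no steroid instruction; it mentions steroids only to define its exception. There is nothing there to contradict.
- *Dose-limiting toxicity counts or dose escalation are compromised.* Section 1.8.6 reports no dose-limiting toxicities to date in Cohorts 1, 2A, 2B and 3. The Amendment 4 rationale (Appendix E) says that enrollment was stopped and that Groups B and C never enrolled. No live effect on escalation, or through Tables 16 and 17, remains.

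The conclusion assumes that some Group A subjects are still on treatment or may be re-treated. The documents do not give their number, or say how many rashes were uncomplicated.

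**What to change.** Amend Tables 15 and 22 as follows.

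1. State that Table 22 governs rash with no other identified cause.
2. Split its Grades 3 and 4 row. Grade 4 rash discontinues pembrolizumab and epacadostat, with exceptions only by medical monitor approval. This matches Table 18, and Table 15 on pembrolizumab.
3. Give one epacadostat restart dose for Grade 3 rash resolved within 4 weeks.
4. Either copy the uncomplicated Grade 3 exception into Table 22 or delete it from Table 15.

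Item 1 alone is not enough, because it would leave Table 22 as the Grade 4 outlier.

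The cost is a short protocol amendment with sponsor and IRB/IEC approval (Section 10.1). The SAP needs no change: Appendix A already lists adverse events, study drug administration and concomitant medications. Table 10, Tables 16 and 17, and the rash wording in Section 4.1.1 can stay as they are, since nothing live depends on them.
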